4 ANALYSIS APPROACH

4.1 ANALYSIS OF THE PRIMARY EFFICACY ENDPOINT

4.1.1 Primary Efficacy Endpoint

The primary endpoint (the proportion of subjects requiring COVID-19 related hospitalization/ER visit or who died due to any cause within 28 days of randomization) will be analyzed using an unadjusted Pearson chi-squared test. If the expected number of events in either group is less than five (5), a Fisher's exact test will be used.

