13.1 Determination of Sample Size

Assuming that the proportions of outpatients who are hospitalized for COVID-19 related disease or die due to any reason within 28 days of randomization are 30% and 15% for placebo and camostat mesilate groups, respectively, based on the two-sided Fisher's Exact Test, at the target significance level of 5%, 275 outpatients (183 in camostat mesilate group and 92 in placebo group) are needed to achieve 80% power. Thus, approximately 300 outpatients (200 in the camostat mesilate group and 100 in the placebo group) will be randomized to account for subject drop-out.

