2.4 RANDOMIZATION

Subjects will be randomized in a 2:1 ratio of Camostat mesilate: placebo. Approximately 300 subjects are planned to be enrolled (200 subjects to Camostat mesilate and 100 subjects to placebo).

One global computer generated, blocked randomization list with 2/3's of the assignments will be to Camostat mesilate and 1/3 to placebo, in random order. Randomization block sizes will randomly vary in size 3 and 6. Labeling will be randomly varied as an additional masking feature.

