4.1.3 Testing of Primary Efficacy Hypothesis

Primary results will include the numbers and percentages of subjects in each treatment group requiring COVID-19 related hospitalization/ER visit or who died due to any cause within 28 days of randomization.

As noted in the next section, the study is statistically powered by assuming that $\pi_{cm} = 0.15$ and $\pi_{pl} = 0.30$ and the number of subjects to be randomized are 186 and 93, in the active and placebo arms, respectively. Consequently, the expected number of subjects to experience the event is nearly 28 for both arms, with 158 and 65 subjects in the active and placebo arms, respectively, not expected to experience the primary endpoint. Therefore, an unadjusted chi-squared test (or exact test, if expected cell counts are < 5 in either group) will be used to test the primary efficacy hypotheses using a two-sided type 1 error of 0.05. Superiority will be concluded if $p < 0.05$ and the proportion of subjects experiencing the event is smaller among subjects randomized to the active treatment. This is tantamount to specifying a one-sided type 1 error rate of $\alpha = 0.025$.

In addition to determining the p-value for the primary efficacy hypothesis, results will also be expressed in terms of a two-sided normal based (asymptomatic) 95% confidence interval estimating the treatment group difference in 28-day COVID hospitalization or death. The upper bound of the confidence interval will be interpreted as the smallest treatment effect consistent with the study results.

If the expected number of events in either group is less than five (5), a Fisher's exact test and exact binomial intervals will be provided.

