4.1.4 Sample Size Determination for the Primary Efficacy Hypothesis

Sample size determination assumed event rates of 15% and 30% in the active and placebo groups, respectively, 2:1 randomization, and a two-sided type 1 error rate of $\alpha=0.05$. Under these assumptions, an adjusted chi-square test will have 80% power for sample sizes of 186 and 93 in the investigational and placebo arms, respectively (total sample size = 279). The sample size is increased by approximately 7.5% to allow for up to 200 and 100, respectively, to account for loss-to-follow-up.

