4.1.6 Handling of Baseline Differences

Group differences in baseline characteristics will be evaluated. Analyses will be performed to evaluate the treatment effect controlling for baseline covariates found to have clinically meaningful baseline differences. Clinically meaningful will be determined by the Sponsor Study Safety Monitor or Primary Investigator. This will be done using a generalized linear model with parameters estimated using SAS PROC GENMOD with distribution set to *binomial* and link set to *logit*. The adjusted probabilities and their standard errors are determined on the probability scale using the *ilink* option in a *lsmeans* statement with a *diff* option. This statement produces a test for the treatment group difference controlling for other covariates in the model. The model will include treatment group and each identified covariate one-at-a-time. The standard error on the probability scale for the difference in event rates will be determined as the square root of the sum of the treatment group specific squared standard errors and used in the determination of the 95% CI.

As requested by FDA, multivariable analyses will be provided to the degree that sample size and number of observed events in each group allow. It is understood that a total of 10 events per covariate is necessary for this modeling approach, which limits the number of covariates the model can support. The full model will consist of age, BMI, sex, and the number of days since first COVID-19 symptom (≤ 5 or > 5 days), in addition to treatment group (sample size permitting). In addition to the full model, a forward stepwise procedure will be used to identify a set of covariates that each provide some independent association with the primary outcome.

The totality of evidence (i.e., the clinical and statistical interpretations) will provide support for decision making regarding Phase III investigation.

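### The unadjusted primary test is valid, but a standardised risk difference using the SAP's own four baseline covariates is a cheap improvement that could add a few points of power

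*SAP*

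**What the plan says.** **Primary test.** The primary endpoint "will be analyzed using an unadjusted Pearson chi-squared test" (SAP 4.1.1), with Fisher's exact test if expected events in an arm fall below five. SAP 4.1.3 repeats this and tests "using a two-sided type 1 error of 0.05". SAP 4.1.2 states the hypothesis as a difference between two marginal probabilities.

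**Randomisation.** SAP 2.4 describes "One global computer generated, blocked randomization list". Neither document names a stratification factor.

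**Missing outcomes.** SAP 4.1.7 imputes 20 data sets from a model with age, BMI, sex, symptom duration and clinic temperatures. It takes a treatment difference and its standard error from each and combines them by Rubin's rule.

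**Adjusted analyses.** SAP 4.1.6 has three: covariates one at a time where a baseline difference is judged clinically meaningful; a fixed model, requested by FDA; and a forward stepwise model. Of the fixed model it says: "The full model will consist of age, BMI, sex, and the number of days since first COVID-19 symptom", split at 5 days, plus treatment. It requires 10 events per covariate. For the covariate-adjusted risk difference it forms the standard error as the root of the summed squared arm-specific errors. Protocol 13.3.1 permits a logistic model but does not require one.

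**Sizing.** "Sample size determination assumed event rates of 15% and 30% in the active and placebo groups, respectively, 2:1 randomization"; on that basis "an adjusted chi-square test will have 80% power for sample sizes of 186 and 93" (SAP 4.1.4). Using Fisher's test, Protocol 13.1 finds that "275 outpatients (183 in camostat mesilate group and 92 in placebo group) are needed to achieve 80% power". The SAP adds: "The sample size is increased by approximately 7.5% to allow for up to 200 and 100, respectively".

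**The concern.** With no strata and no covariates in the primary comparison, any chance imbalance in age or BMI passes straight into the estimate. Randomisation makes that fair on average and the standard error allows for it, so nothing is biased. What is lost is precision: outcome variation that baseline data could explain stays in the error term. Protocol 5.1.1 says that age 65 or over, obesity and several comorbidities contribute to worse disease, so some explainable variation is plausible.

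The supportive analyses do not recover that precision:

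- The SAP 4.1.6 standard error treats the two adjusted probabilities as independent. They share an intercept and covariate coefficients, so a covariance term is missing.
- Inverse-link least-squares means are probabilities at a reference covariate profile, not averages over the patients.
- Two of the three covariate choices depend on the data.
- Table shell 14.2.1.4, which reports the adjusted results, footnotes its p-value as an unadjusted chi-square.

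No rule says which result prevails if the adjusted and unadjusted analyses differ, although both feed the Phase III decision.

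**Working it through.** **1. The plan's own figure.** Exact binomial enumeration, 30% versus 15%, two-sided 0.05:

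| Sample size | Test | Power |
|---|---|---|
| 186:93 (SAP) | Continuity-corrected chi-square | 78.9% |
| 186:93 | Fisher | 80.2% |
| 186:93 | Pearson, uncorrected | 83.0% |
| 183:92 (protocol) | Fisher | 80.2% |

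The stated 80% is reproduced. Inflation: 279 × 1.075 = 299.9, about 300.

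**2. The planned Pearson test at 200:100.** The pooled rate is (30 + 30)/300 = 0.20.

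- Null SE = √[0.20 × 0.80 × (1/100 + 1/200)] = 0.0490
- Alternative SE = √[0.30 × 0.70/100 + 0.15 × 0.85/200] = 0.0523
- Power = Φ[(0.15 − 1.96 × 0.0490)/0.0523] = Φ(1.03) = 84.9% (85.3% exact)

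Because the smaller arm has the higher rate, the unpooled SE (0.0523) exceeds the pooled SE (0.0490). A Wald test of the difference is therefore weaker than Pearson. This matters because combining a difference and its SE over imputed data sets, as in SAP 4.1.7, is a Wald-type test. The SAP does not state the SE form; I assume unpooled. Pearson applies directly only when nothing is missing.

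**3. Effect of adjustment.** Assumptions: two standard normal covariates (age, BMI), sex 50:50, 40% with symptoms beyond 5 days, equal strength per SD, marginal rates held at 30% and 15%, no missing data, 8,000 trials per row. Neither document gives an R², AUC or odds ratio, so strength is varied.

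The standardised difference is d = mean(m1 − m0), where m1 and m0 are each patient's fitted risks under camostat and placebo. With T the treatment indicator and π = 2/3, the influence value is IF = T(Y − m1)/π − (1 − T)(Y − m0)/(1 − π) + m1 − m0 − d, and SE² = ΣIF²/[n(n − 6)].

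| OR per SD | Placebo-arm R² | Pearson % | Wald % | Standardised % | vs Wald | vs Pearson |
|---|---|---|---|---|---|---|
| 1.00 | 0.00 | 85.7 | 83.2 | 83.0 | −0.2 | −2.7 |
| 1.28 | 0.05 | 85.2 | 82.9 | 84.0 | +1.1 | −1.2 |
| 1.45 | 0.10 | 85.3 | 83.2 | 85.7 | +2.5 | +0.4 |
| 1.65 | 0.16 | 85.6 | 83.4 | 88.4 | +5.0 | +2.8 |
| 1.87 | 0.22 | 85.6 | 83.5 | 90.5 | +7.0 | +4.9 |

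In the first row, 2.5 of the 2.7 points lost to Pearson come from the Wald form (85.7 − 83.2). Only 0.2 comes from fitting useless covariates.

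One-sided type I error of the standardised test was 0.023 (R² 0) and 0.025 (R² 0.16) at a common 30% rate. It was 0.019 to 0.029 in 3,000-trial runs at a common 20% rate.

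**4. The SAP 4.1.6 method as written.** A separate run used 3,000 trials per setting, with log-odds per SD of 0, 0.25, 0.4 and 0.6. The 4.1.6 form gave 81.9, 83.5, 83.5 and 84.6%; the standardised difference gave 82.1, 84.6, 86.3 and 90.1%. At the strongest setting, with Wald at 82.4%, the gain is 2.2 points instead of 7.7.

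**5. Events.** At 279: 186 × 0.15 + 93 × 0.30 = 55.8, about 56. At 10 each that supports five terms, exactly treatment plus four covariates. At 300 there are 60.

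If rates were 10% and 5%, 300 patients give 10 + 10 = 20 events, enough for two terms. Power there (R² 0 and 0.05) was 37.9 and 38.7% for Pearson, 29.0 and 28.7% for Wald, and 29.3 and 31.3% for the standardised difference. Without a fallback the change would cost 7 to 9 points against Pearson.

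**The case against.** The case for leaving the plan alone is substantial. An unadjusted test under unstratified randomisation is valid and standard, and it matches the stated hypothesis. Pearson already has about 85% power at 300. With covariate strength unknown, even the sign of the change against Pearson cannot be settled from the documents; break-even lies near R² 0.10. Every participant must have a risk factor (Protocol 8.1), and SAP 3.1 counts any hospitalisation or ER visit on the End of Study form as a failure; both may weaken prediction within the trial. The comorbidities listed in Protocol 5.1.1 are not in the four-covariate model. Entry requires a positive test and an oxygen saturation threshold but not symptoms, so some patients may have no onset date. The events rule is only just met.

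All of this stands as a limit on size and as a reason for a fallback. It does not defeat the change, which uses covariates the SAP has already fixed, keeps the marginal risk-difference question, and replaces what is already a Wald-type test whenever outcomes are imputed.

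A reader might also infer from *adjusted* in SAP 4.1.4 that the trial was sized on a covariate-adjusted test. The figures do not support that: 80% at 186:93 fits a continuity-corrected or Fisher test with no covariates. The clash with *unadjusted* in 4.1.1 and 4.1.3 is a separate wording point.

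**Conclusion.** The point holds as a cheap improvement in efficiency and pre-specification. At 200:100 and the planned rates, the standardised estimate changes power by about 0 to +7 points against the unpooled Wald test and about −3 to +5 against Pearson, with type I error held. These figures rest on assumed covariate strength (R² 0 to 0.22), an assumed unpooled SE, and no missing data.

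Four stronger readings are tempting, and the documents do not support them:

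- **That the primary test is wrong or biased.** It is neither.
- **That the plan ignores the covariates or adjusts only for observed imbalance.** They enter the imputation model, and SAP 4.1.6 fixes a full model whatever the imbalance.
- **That all four are named as prognostic.** Protocol 5.1.1 supports age and obesity. It does not name sex, and it ties symptom duration only to when deterioration occurs.
- **That adjustment is free.** Useless covariates lose up to about 3 points to Pearson, and with event rates far below plan there is no gain over it.

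**What to change.** Amend the SAP before unblinding:

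- **Primary estimate.** Use the standardised (g-computation) risk difference from a logistic model with treatment, age, BMI, sex and symptom days (≤5 versus >5), with an influence-function standard error. Compute it in each imputed data set and combine by Rubin's rules. Take the 4.1.3 confidence interval from the same estimate.
- **Supportive analyses.** Keep the unadjusted chi-square as the first sensitivity analysis. Drop the root-sum-of-squares standard error in 4.1.6 and correct the p-value footnote in table shell 14.2.1.4.
- **Fallback, fixed in advance on blinded pooled events.** Below about 50 events, use treatment, age and BMI only. If there are too few for that under the 10-per-covariate rule (30, counting treatment as a term), or if the exact-test branch applies, use the unadjusted or Fisher test as now written. The range from 30 to 50 events was not simulated.
- **Symptom days.** State how patients with no symptom onset date are coded.

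The cost is SAP text and modest programming, with no new data. The statistical price is the possible loss of up to about 3 points against Pearson.

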4.1.2 Primary Efficacy Hypotheses

The primary efficacy hypothesis is that the probability of experiencing a COVID-19 related hospitalization/ER visit or death from any cause within 28 days of randomization is smaller among subjects randomized to the study drug relative to those subjects randomized to placebo. Symbolically, these hypotheses may be represented as follows.

$$H_0: \pi_{cm} - \pi_{pl} \geq 0$$

$$H_a: \pi_{cm} - \pi_{pl} < 0$$

Where π_{cm} and π_{pl} are the probabilities of experiencing the primary endpoint as defined above among subjects randomized to Camostat mesilate and placebo, respectively.

4.1.3 Testing of Primary Efficacy Hypothesis

Primary results will include the numbers and percentages of subjects in each treatment group requiring COVID-19 related hospitalization/ER visit or who died due to any cause within 28 days of randomization.

As noted in the next section, the study is statistically powered by assuming that $\pi_{cm} = 0.15$ and $\pi_{pl} = 0.30$ and the number of subjects to be randomized are 186 and 93, in the active and placebo arms, respectively. Consequently, the expected number of subjects to experience the event is nearly 28 for both arms, with 158 and 65 subjects in the active and placebo arms, respectively, not expected to experience the primary endpoint. Therefore, an unadjusted chi-squared test (or exact test, if expected cell counts are < 5 in either group) will be used to test the primary efficacy hypotheses using a two-sided type 1 error of 0.05. Superiority will be concluded if $p < 0.05$ and the proportion of subjects experiencing the event is smaller among subjects randomized to the active treatment. This is tantamount to specifying a one-sided type 1 error rate of $\alpha = 0.025$.

In addition to determining the p-value for the primary efficacy hypothesis, results will also be expressed in terms of a two-sided normal based (asymptomatic) 95% confidence interval estimating the treatment group difference in 28-day COVID hospitalization or death. The upper bound of the confidence interval will be interpreted as the smallest treatment effect consistent with the study results.

If the expected number of events in either group is less than five (5), a Fisher's exact test and exact binomial intervals will be provided.

4.1.4 Sample Size Determination for the Primary Efficacy Hypothesis

Sample size determination assumed event rates of 15% and 30% in the active and placebo groups, respectively, 2:1 randomization, and a two-sided type 1 error rate of $\alpha=0.05$. Under these assumptions, an adjusted chi-square test will have 80% power for sample sizes of 186 and 93 in the investigational and placebo arms, respectively (total sample size = 279). The sample size is increased by approximately 7.5% to allow for up to 200 and 100, respectively, to account for loss-to-follow-up.

4.1.5 Heterogeneity of Treatment Effects

Heterogeneity of treatment effects will be evaluated for the subgroups (see [Subgroup Analyses](#)). To this end, the estimated group difference in the probability of experiencing the event on the probability scale, along with its 95% confidence interval (CI) will be estimated within each subgroup. These results will be graphically displayed in a forest plot.

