4.4 SUBGROUP ANALYSES

Exploratory pre-specified subgroup analysis will be performed. For these exploratory analyses, primary efficacy endpoint, selected secondary efficacy endpoints, and selected safety endpoints will be repeated and stratified according to the following classifications:

1. Days from first COVID-19 symptom to the start of treatment, ≤ 5 days or > 5 days
2. Age, <55 and ≥ 55 years
3. Age, <65 and ≥ 65 years
4. Age, ≥ 75 years
5. Sex at birth
6. Race, White vs. non-white
7. Ethnicity, Hispanic vs. non-Hispanic
8. Number of Risk Factors
9. Site (see [Site Poolability](#))
10. Region (see [Region Poolability](#))

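### SAP 4.1.5 sets out to evaluate heterogeneity of the treatment effect but, for the patient-characteristic subgroups, plans only within-level intervals and no comparison between levels

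*SAP*

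**What the plan says.** SAP 4.1.5 opens with the aim: "Heterogeneity of treatment effects will be evaluated for the subgroups". The method offered for that aim is the group difference on the probability scale, which, "along with its 95% confidence interval (CI) will be estimated within each subgroup", is then drawn in a forest plot. The section specifies nothing else.

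SAP 4.4 introduces the subgroups with "Exploratory pre-specified subgroup analysis will be performed" and says that the primary endpoint and selected other endpoints "will be repeated and stratified according to the following classifications". Ten classifications follow:

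- Six are explicit two-level factors: symptom duration (5 days or less vs more), age at 55, age at 65, sex, race and ethnicity.
- Age 75 or over is listed without a comparison level, although the draft demographic table shows the under-75 group.
- Number of risk factors, site and region complete the list. The draft table gives risk-factor count six levels and region four.

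The forest-plot entries in the SAP's table list (Tables 14.2.1.7 to 14.2.1.9) name group differences with 95% intervals and no interaction estimate.

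Site is treated differently. SAP 4.6.1 gives a random-effects meta-analysis with I-squared and, if site variability is significant, a random-effects logistic regression. Region (4.6.2) has only a summary of its distribution.

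**The concern.** Heterogeneity is a difference between levels in the treatment effect. An interval within one level says whether that level's effect is distinguishable from zero, so a set of such intervals does not estimate what 4.1.5 sets out to evaluate. The aim and the method do not match, whatever the numbers turn out to be.

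The practical risk lies in how the forest plot is read. The trial is sized for about 80% power overall, so each subgroup level has much less. With a perfectly uniform benefit, one level will often exclude zero while its partner does not, and the plot invites the conclusion that the drug works in one and not the other. Symptom duration is an obvious candidate: it is first in the SAP 4.4 list, and protocol section 5.1.1 argues for an early window for antiviral treatment. A reader could come away with an early-versus-late story that the data do not support.

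**Working it through.** **Inputs.** From SAP 4.1.4: "Sample size determination assumed event rates of 15% and 30% in the active and placebo groups, respectively, 2:1 randomization". From SAP 4.1.3, the test is run "using a two-sided type 1 error of 0.05". From SAP 2.4: "Approximately 300 subjects are planned to be enrolled (200 subjects to Camostat mesilate and 100 subjects to placebo". The documents give no subgroup shares. Those used here are assumptions: 50/50 to 80/20, with 90/10 as an extreme, and age shares from a normal distribution with mean 48-50 and SD 13-14 years.

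**The plan's own figure.** SAP 4.1.4 says "an adjusted chi-square test will have 80% power for sample sizes of 186 and 93 in the investigational and placebo arms". Exact enumeration at 186/93 gives 78.9% for the continuity-corrected chi-square, 80.2% for Fisher and 83.0% for the uncorrected Pearson test. The stated 80% therefore reproduces to within about one point for the corrected test. The inflation also checks: 186 × 1.075 ≈ 200 and 93 × 1.075 ≈ 100.

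**One two-level factor, uniform effect.** For a level holding share *s* of 200 + 100 subjects:

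SE(s) = √[0.15 × 0.85/(200s) + 0.30 × 0.70/(100s)]; power(s) = Φ(0.15/SE(s) − 1.96)

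At s = 0.5, SE = √(0.001275 + 0.0042) = 0.0740 and power = Φ(2.027 − 1.96) = 0.527.

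The levels are independent, so P(discordant) = a(1 − b) + b(1 − a), where a and b are the two powers. At 50/50 this is 2 × 0.527 × 0.473 = 0.499.

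| Split | Power, smaller level | Power, larger level | Discordant |
|---|---|---|---|
| 50/50 | 0.527 | 0.527 | 0.499 |
| 40/60 | 0.442 | 0.603 | 0.512 |
| 30/70 | 0.348 | 0.670 | 0.551 |
| 20/80 | 0.249 | 0.727 | 0.614 |
| 10/90 | 0.146 | 0.776 | 0.696 |

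Half of trials are discordant even when neither level is smaller. The main cause is therefore low power within each level; unequal splits make it worse.

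**Several factors.** All factors re-use the same outcomes, so multiplying probabilities overstates the result: 1 − 0.5³ = 0.875 for three factors, against 0.752 by simulation. Simulated trials (5,000 per even-split scenario, Wald intervals, 200/100, same true effect everywhere) gave the following for at least one discordant factor at 30% vs 15%:

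- 86% with 6 even factors, 88% with 7 and 90% with 8;
- 90% with 6 unequal factors;
- 92% with 6 factors including the age 55 and 65 cuts, and 93-94% with 7 including age 75.

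**Other uniform truths, 6-7 two-level factors.** 80-81% at 20% vs 10%; 53-59% at 10% vs 5%; 35-45% with no effect (20% in both arms).

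**A direct contrast instead.** Take z = (D₁ − D₂)/√(SE₁² + SE₂²), where D is a level's risk difference. Its false-positive rate is about 5-6% per balanced factor. For at least one factor, unadjusted, it is 28-32% with 6-7 factors and 36% with 8. Bonferroni brings it to about 6-7%. The Wald form is anti-conservative in very small levels: 13-20% for age 75, which takes the rate for at least one factor to about 40-42%.

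**Precision of that contrast.** At 50/50 the SE of D₁ − D₂ is √2 × 0.0740 = 0.105, so the 95% half-width is 1.96 × 0.105 ≈ 0.205. At 80/20 it is 1.96 × √(0.1170² + 0.0585²) ≈ 0.256. Both exceed the whole assumed effect of 0.15.

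**The case against.** The strongest reply is that the SAP plans a display, not an inference. Nowhere does it say that a subgroup difference will be declared because one interval excludes zero and another does not. A reader might infer that the plan itself would announce subgroup differences in nine of ten uniform trials; the documents do not support that. The figure measures a common misreading. Under another visual rule, non-overlapping intervals, it would be only about 4-17% at the design rates. This stands, and the size must be stated conditionally.

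Three further points also stand:

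- SAP 4.4 already labels the subgroup analyses exploratory.
- It would be wrong to say that no listed factor has a heterogeneity method, because site has one in 4.6.1.
- A reader might infer from SAP 4.1.6 that the subgroup plots will decide the Phase III population. The totality-of-evidence sentence there closes a section on baseline covariate adjustment and covers clinical as well as statistical interpretation. It does not tie Phase III to subgroups, and no passage singles out symptom duration for that role.

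Nor is an interaction contrast a cure: unadjusted, it still flags something in roughly a third of uniform trials.

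None of this makes within-level intervals an estimate of heterogeneity. An exploratory label lowers the stakes but supplies neither the missing contrast nor a reading rule.

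**Conclusion.** The point holds as a mismatch between aim and method in SAP 4.1.5, confined to the patient-characteristic factors and region; site is the exception. At the design rates with a uniform effect, discordant intervals occur in about 50-62% of trials per two-level factor and in about 85-95% for at least one of 6-8 factors. These figures rest on assumed subgroup shares, on the true rates being 30% and 15%, and on a reader treating discordance as a difference. Smaller uniform effects, or none, bring the figure for at least one factor down to between 35% and 81% over the scenarios checked.

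The consequence is possible misreading of an exploratory forest plot. The primary test, its type 1 error and the sample size are untouched. This is a worthwhile improvement, not a defect that must be corrected.

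**What to change.** Keep the forest plot and add to SAP 4.1.5:

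- For each two-level factor, the between-level difference in risk difference with its 95% CI and interaction p-value. Use under 75 as the comparator for age 75 or over.
- For factors with more than two levels (risk-factor count, region), a single global interaction test. Site stays with 4.6.1.
- An exact or model-based method where a level is very small, since the Wald contrast is unreliable there.
- A statement that heterogeneity is judged on these contrasts and not on which intervals cross zero, and that they are exploratory and unadjusted for multiplicity.

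The cost is an extra column in the planned plot, a global test for two factors and a few sentences of SAP text; no new data are needed. The SAP should state the downside: at N = 300 the contrasts have low power, so a non-significant result is not evidence of a uniform effect. Without multiplicity adjustment they will also flag at least one factor in about 30-40% of trials whose effect is uniform.
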